9.4. INFORMED CONSENT

If the patient decides to participate, the patient information sheet will be given to the patient, and after reading the document and clarifying any doubts, if they agree to participate in the study, the patient will sign the informed consent.

10. STATISTICAL ANALYSIS PLAN AND SAMPLE SIZE

10.1 STATISTICAL ANALYSIS

A descriptive analysis of both cohorts defining their clinical and angiographic profiles and a comparative study of the two groups (cohorts) will be performed. The categorical variables are expressed in percentages and the continuous as medium value \pm standard deviation. The relative risk and the “Hazard Ratio” will be used as measures of effect when variables are analyzed with a temporal component, always with a confidence interval of 95%. For the comparison of categorical variables, the Chi-square or the Fisher test will be used. To compare continuous variables, the “t” of student test or analysis of variance will be used. The variables of time to event, such as the analysis of event-free survival will be analyzed by using the Kaplan- Meier technique and will be supplemented by the log-rank test. The multivariate analysis of the adverse events predictors during the follow-up will be done by means of the Cox regression model, determining the Odds Ratio for each variable.

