vessels during the procedure but also those occurred in the monitoring where there is still no solid evidence regarding antithrombotic handling. 2, Atrioventricular conduction disorders requiring permanent pacemaker implantation in 20-40% of the patients. 3, Vascular complications of the accesses. 4, Residual valve by the malpositioning of the prosthesis (creating a high residual gradient or insufficiency). 5, Valvular degeneration and durability of the prosthesis.

Cardiac amyloidosis by transthyretin.

The amyloid myocardial infiltration by transthyretin monomers and oligomers (TTR) with misfolding(7) is a serious and under-diagnosed disease which predominantly affects men over 60 years old and presents itself with symptoms of heart failure, orthostatic hypotension, and syncope (8). The infiltration of the cardiac conduction system can generate branch blocks, atrioventricular blocks, and atrial fibrillation.

There are two types of amyloid that can infiltrate the myocardium: the amyloid light chain (AL or primary) within a monoclonal gammopathy, and the TTR amyloid. The latter in turn has two types of disease, familial, due to a mutation that causes transthyretin misfolding; and sporadic (formerly known as senile), which is due to incorrect folding of the common transthyretin. (8)

The prevalence of the TTR amyloidosis in patients with AoS to whom a TAVI is performed is estimated at 14-16%(9)(10) and 6% in those over 65 years old to whom a surgical valve replacement is performed(11). It is especially associated with the AoS phenotype of low-flow and low gradient (9). Cardiac amyloid deposits were found in nearly one-third of autopsies of patients with TAVI implants who died before 30 months(12), and the patients with AoS and amyloidosis have a prognosis similar to those with amyloidosis without AoS (13). It all states that the amyloidosis implies a worse prognosis (11). It is also suggested that amyloid infiltration may increase the requirements of permanent pacing (14).

Recently the benefits of treatment with Tafamidis on patients with cardiac amyloidosis by TTR have been published. (15)

Non-invasive diagnosis of cardiac amyloidosis.

The echocardiogram is used to find interesting data of amyloidosis: increased thicknesses of the atrioventricular valves, interatrial septum valves or the free wall of

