10.1 SAMPLE SIZE

Based on the information available, around 15% of the patients to whom a TAVI has been implanted show signs of amyloidosis. Mortality at two years after a TAVI is about 17% and in patients with amyloidosis, it is estimated to be 40%. Based on this data, for a significance level of 5% (error $\alpha = 0,05$) and a power of 80% (error $\beta = 0,20$), a sample size of 306 patients is estimated, assuming 5% of follow-up losses, it was decided to include 321 patients. The results in which the calculations are based are given at 2 years, if not significant; monitoring would continue up to 3 years.

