11. PATIENTS FOLLOW-UPS

11.1 INITIAL PATIENT ASSESSMENT

An initial inclusion visit will assess whether the patient is a candidate who meets the inclusion criteria and none of the exclusion ones. After being informed, if they accept, the informed consent must be signed. The following data must be recorded:

- **Clinical parameters:** age, sex, height, weight, body mass index, body surface, cardiovascular risk factors, medication intake, background interests, history of heart disease, presence of ischemic heart disease, cerebrovascular accident, peripheral artery disease, chronic obstructive pulmonary disease, symptoms (angina, syncope, dyspnea according to grades of the NYHA, other symptoms), blood pressure, heart rate, evidence of heart failure, assessment of functional class by means of 6MT and fragility assessment.
- **Analytical parameters:** hematocrit, NT-proBNP, Troponin I, electrolytes, C-reactive protein, creatinine, glomerular filtrate.
- **Protein electrophoresis:** Rating presence of the monoclonal component
- **Scintigraphy with TC⁹⁹:** Assessment of values of tracer uptake.
- **Device parameters:** Type of prosthesis, dimensions, expandable/ self-expanding ball, post-dilatation.
- **ECG parameters:** Rhythm, PR duration, pacemakers, implantable cardioverter defibrillator, QRS duration.

- The 6 minute-test: All patients in the study will have a test of 6 minutes before implantation and 6 months follow-up, according to the protocol after a TAVI, in order to carry out an objective functional assessment of the functional capacity. The distance covered will be determined, the variation of oxygen saturation by means of non-invasive pulse oximetry before and after the test and the appearance of symptoms with the effort according to the Borg scale.

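### Student's t test is the only two-group test named for continuous variables; at about 48 v 273 patients it is sensitive to unequal spread, and on raw values it loses power if markers are strongly skewed

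*Combined protocol and SAP*

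**What the plan says.** Section 10.1 (Statistical Analysis) gives one rule for all continuous variables. For description: "The categorical variables are expressed in percentages and the continuous as medium value", plus or minus the standard deviation; I read this translated phrase as the mean. For comparison, the t "of student test or analysis of variance will be used". The rule is not confined to the baseline table. Nowhere do the documents mention an unequal-variance test, a transformation, a median with IQR, a rank test or a check of assumptions.

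The variables it would cover include:

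- 6-minute walk distance, the measure for secondary objective 2;
- strain values, which underlie secondary objective 3;
- laboratory markers listed in Section 11.1, among them "hematocrit, NT-proBNP, Troponin I, electrolytes, C-reactive protein", and collected again at follow-up under Sections 11.2 and 12. No objective names these markers.

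On cohort sizes, Section 10.1 (Sample Size) says that "around 15% of the patients to whom a TAVI has been implanted show signs of amyloidosis" and that "it was decided to include 321 patients". Section 4 says that the prevalence "is estimated at 14-16" per cent.

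**The concern.** Student's t test, in its usual form, pools the two variances. With cohorts of similar size, a difference in spread does little harm. With about 1 patient in the small cohort to 5.7 in the large one, the pooled variance is almost entirely that of the large cohort, whereas the true uncertainty of the difference comes mostly from the small one. If the amyloidosis cohort is more variable, the standard error is too small and the test rejects too often. If it is less variable, the standard error is too large and real differences are missed.

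The second issue is separate. If a marker is strongly right-skewed, a comparison of raw means is dominated by a few high values and has less power than the same comparison on logs. A mean with SD also describes such a variable poorly.

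At stake are the p-values and confidence intervals for walk distance and for any comparison of strain between cohorts, and the ability to detect marker differences.

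**Working it through.** **Cohort sizes.** 306 × 1.05 = 321.3, which matches the planned 321. (The 306 is close to the 299 from a log-rank formula with hazard ratio ln 0.60 / ln 0.83 = 2.74 and 61 events over an event probability of 0.2045. The plan does not name its formula, and nothing below depends on it.) Then 0.15 × 321 ≈ 48 and 0.85 × 321 ≈ 273. Shares of 14% and 16% give 45/276 and 51/270.

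**Part 1: unequal spread, equal means.** Let k be the SD of the small cohort divided by that of the large one, with the large SD set to 1. The documents do not give k; the values below are assumptions.

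- True variance of the difference: k²/48 + 1/273.
- Variance the pooled test uses on average: [(47k² + 272)/319] × (1/48 + 1/273).
- q = square root of true over used. Large-sample two-sided type I error = 2 × [1 − Φ(1.96/q)].

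For k = 1.5: true 0.0505; used 1.184 × 0.0245 = 0.0290; q = 1.32; 1.96/1.32 = 1.485; type I error 13.8%.

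| k | Formula | Student, simulated | Welch, simulated |
|---|---|---|---|
| 0.5 | 0.2% | 0.2% | 5.0% |
| 1 | 5.0% | 4.9% | 5.0% |
| 1.25 | 9.3% | 9.4% | 5.1% |
| 1.5 | 13.8% | 13.7% | 5.0% |
| 2 | 21.2% | 21.3% | 4.8% |

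(Normal data, 48 v 273, 20,000 runs, nominal 5%.) Shares of 14% to 16% move the k = 1.5 figure only from 14.1% to 13.5%.

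**Part 2: skewness alone.** With the same lognormal distribution in both cohorts (log-SD 0.5 to 1.5), raw Student's t rejects 4.7% to 5.0% of the time. Skewness without a difference in spread does not inflate type I error at these sizes.

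**Part 3: power for a skewed marker.** Lognormal values, equal log-SD σ, geometric mean ratio 1.5; both inputs are assumed. On logs, power ≈ Φ[ln 1.5 / (σ√(1/48 + 1/273)) − 1.96]. For σ = 1.0 this is Φ(0.4055/0.1565 − 1.96) = Φ(0.63) ≈ 74%, in line with the simulated 73%.

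| Log-SD | Student, raw | Student, logs | Welch, logs | Welch, raw |
|---|---|---|---|---|
| 0.8 | 82% | 90% | 89% | 72% |
| 1.0 | 60% | 73% | 72% | 40% |
| 1.2 | 42% | 58% | 57% | 19% |
| 1.5 | 27% | 41% | 40% | 6% |

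At log-SD 0.5 a ratio of 1.5 is detected almost always either way; for a ratio of 1.25 the figures are 78% raw and 81% on logs.

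**Part 4: candidate remedies.** Welch's test on raw skewed values is not a remedy: with identical lognormal distributions its type I error is 7.4% at log-SD 1.0 and 10.4% at 1.5, and its power is the lowest in the table. Student's t on logs still drifts if the log-SDs differ (8.1%, 13.8% and 21.0% at log-SD ratios 1.2, 1.5 and 2). So does the Mann-Whitney test (6.1%, 8.8% and 11.5%). Welch's test on logs gives 4.7% to 5.1% throughout.

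**The case against.** The strongest reply is that the documents give no reason to expect unequal spread at equal means. They state no SD, distribution or expected difference for any continuous variable, and nothing says that walk distance is more variable with amyloidosis. That stands: every SD ratio, log-SD and geometric mean ratio above is an assumption, and the error could run in either direction. It does not remove the point, because the equal-variance assumption is equally unsupported and is costly to get wrong at this split.

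A reader might infer that the plan will produce many false-positive marker findings. The documents do not support that. If NT-proBNP is both higher and more variable in amyloidosis, rejecting equality is correct; for such a marker the harm is lost power and a poor interval. The 9% to 21% figures apply only where means are equal and spreads differ.

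A reader might also place NT-proBNP, troponin and C-reactive protein among the secondary objectives. They are recorded parameters only. Objective 2 clearly calls for a continuous comparison between cohorts. Objective 3 is mainly about validating a strain pattern against the diagnosis, so the t test matters there only if strain values are compared between cohorts.

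Two further replies have less force. The text does not say that variances are pooled, but that is the ordinary meaning of Student's test, and one sentence would settle it. And 48 and 273 are baseline numbers. Section 10.1's mortality figures ("Mortality at two years after a TAVI is about 17% and in patients with amyloidosis, it is estimated to be 40" per cent) would leave about 48 × 0.60 = 29 and 273 × 0.83 = 227 at two years before other losses. The same formula then gives 15% rather than 14% at k = 1.5, so attrition does not weaken the point.

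**Conclusion.** The point holds as a modest, inexpensive improvement. Read as the pooled-variance version, the one test named for two-cohort comparisons of continuous variables is sensitive to unequal spread at the plan's own allocation: type I error of about 9%, 14% and 21% at assumed SD ratios of 1.25, 1.5 and 2, and about 0.2% at 0.5. For strongly right-skewed markers, raw-scale testing costs roughly 8 to 16 points of power at log-SD 0.8 to 1.5 and a geometric mean ratio of 1.5, and little at log-SD 0.5.

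It does not follow that skewness by itself makes the p-values wrong, or that the primary result is at risk: time-to-event outcomes go to Kaplan-Meier, log-rank and Cox analyses, which the choice of t test does not touch.

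**What to change.** In Section 10.1 (Statistical Analysis):

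- Use Welch's t test, with its confidence interval, for approximately symmetric measures such as 6-minute distance and strain.
- For NT-proBNP, troponin, C-reactive protein and any other clearly right-skewed variable (creatinine may be one), report median (IQR) or geometric means, and compare cohorts by Welch's t test on log values, not raw values. Report the result as a ratio of geometric means with its 95% interval.
- If these markers enter the Cox model, enter them log-transformed.
- List before analysis which variables are logged.

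Section 11.1 lists Troponin I and the footnote to Section 12 lists TnT. These must be reconciled before troponin values are summarised or logged together.

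The cost is SAP wording; no new data are needed. When variances are equal, Welch's test gives up about 1 point of power (80.7% v 81.5% for a 0.45 SD difference; at most 1.1 points in the lognormal simulations on logs). Log-scale results are read as ratios rather than mean differences.

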 1. DATA COLLECTION
 2. DATA MANAGEMENT
 3. DATA CONFIDENTIALITY
14. PRACTICAL USE OF THE RESULTS
15. ETHICS
16. ANNEX
 1. ECHOCARDIOGRAPHY PROTOCOL
 2. SCINTIGRAPHY PROTOCOL
 3. DECLARATION OF HELSINKI

1. STUDY SUMMARY

Study title and code	Prognostic impact of cardiac amyloidosis in patients with severe aortic stenosis who underwent percutaneous implantation of an aortic prosthesis (AMY-TAVI)
Study type and design	Observational analytical of multicenter prospective cohorts.
Number and characteristics of patients	321 patients to whom a TAVI has been implanted by severe degenerative AoS.
Study duration	Recruitment period: All the consecutive patients to whom a non-invasive diagnostic study of amyloidosis (scintigraphy with tecnecio ⁹⁹ pyrophosphate and electrophoresis of proteins in the blood) and to whom a percutaneous aortic prosthesis for severe aortic stenosis has been implanted. Follow-up period: clinical and echocardiographic monitoring will be done before discharge, in consultation at three, six, twelve, and twenty-four months. Inclusion: 1 year Follow-up: 2 years Data analysis: 6 months Total: 3 years and 6 months
Events	Main event: cardiovascular events (cardiovascular death, stroke, heart attack), death from any cause, readmission for cardiac insufficiency, pacemaker implantation, functional assessment
Participating countries and centers	Various Spanish and international centers will be invited to participate.

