8. OBJECTIVES

8.1 PRIMARY OBJECTIVE

A multicentre prospective study of cohorts consisting of two cohorts from patients who have been implanted with percutaneous aortic prosthesis as treatment for the severe degenerative aortic stenosis and compare the overall mortality and that for

cardiovascular and admissions for heart failure in the 2-year follow-up of patients diagnosed with amyloidosis (by GT99 and EFP) versus those that do not have it.

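### Kaplan-Meier is assigned to time-to-event outcomes with no rule for competing death; heart-failure admission or cardiovascular death analysed alone would have its 2-year risk overstated, probably more with amyloid

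*Combined protocol and SAP*

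**What the plan says.** Section 10.1 (Statistical analysis) states: "The variables of time to event, such as the analysis of event-free survival will be analyzed by using the Kaplan- Meier technique", supplemented by the log-rank test. For predictors it adds: "The multivariate analysis of the adverse events predictors during the follow-up will be done by means of the Cox regression model". Event-free survival is offered as an example and is not defined. No section gives a censoring rule, a rule for death before a non-fatal event, or a cumulative incidence method.

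The primary objective (section 8.1) compares overall mortality together with "cardiovascular and admissions for heart failure in the 2-year follow-up of patients diagnosed with amyloidosis" against patients without it. The study summary lists "death from any cause, readmission for cardiac insufficiency, pacemaker implantation" among the items under a single main event. Neither place says whether heart-failure admission is analysed alone or combined with death.

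The sample-size paragraph (also numbered 10.1) puts 2-year mortality after TAVI at about 17% and says that "in patients with amyloidosis, it is estimated to be 40"%. If the 2-year result is not significant, follow-up would run to 3 years.

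**The concern.** A patient who dies without a heart-failure admission can no longer be admitted. Kaplan-Meier with that death censored treats the patient as still able to have the event later. Read as a 2-year risk, 1-KM is then too high. The same holds for cardiovascular death when non-cardiovascular deaths are censored.

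The plan expects far more deaths in one cohort than in the other, so the error would probably differ between the curves being compared. If admissions are also more frequent with amyloid, the absolute gap would probably be drawn too wide, in the direction of the study hypothesis. Section 14 intends the results to guide screening and early treatment, for which absolute risks matter.

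**Working it through.** **The plan's own figure.** The sample size rests on mortality alone. The plan names no formula; Schoenfeld's comes close.
- Hazard ratio = ln(0.60)/ln(0.83) = 2.74.
- Events = (1.960 + 0.842)² / [0.15 × 0.85 × (ln 2.74)²] = 60.5, so 61.
- Mean event rate = 0.85 × 0.17 + 0.15 × 0.40 = 0.2045, and 61/0.2045 gives 299, against the stated 306.
- 306 × 1.05 = 321.3, the stated 321.

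Heart-failure admission does not enter, so this point does not touch the sample size.

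**Inputs for the bias.**
- From the plan: 2-year mortality of 40% with amyloid, and 17%, taken here as the rate without amyloid. Death hazards λ are −ln(0.60)/2 = 0.2554 and −ln(0.83)/2 = 0.0932 per year.
- Assumed: 2-year 1-KM for admission of p = 10%, 20% or 30%, so h = −ln(1−p)/2 = 0.0527, 0.1116 or 0.1783 per year.
- Assumed: a share s of the death hazard, from 0.5 to 1, acts before a first admission. The share is the same in both cohorts; hazards are constant and independent.

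**Formula.** True cumulative incidence at 2 years = h/(h + sλ) × [1 − exp(−2(h + sλ))]. The overstatement is p minus this.

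| 1-KM | s | Amyloid: true % (excess, points) | No amyloid: true % (excess, points) |
|---|---|---|---|
| 10% | 1 | 7.87 (2.13) | 9.14 (0.86) |
| 10% | 0.5 | 8.84 (1.16) | 9.56 (0.44) |
| 20% | 1 | 15.81 (4.19) | 18.31 (1.69) |
| 20% | 0.5 | 17.73 (2.27) | 19.13 (0.87) |
| 30% | 1 | 23.85 (6.15) | 27.52 (2.48) |
| 30% | 0.5 | 26.68 (3.32) | 28.72 (1.28) |

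**Effect on the gap.** Assume the admission hazard doubles with amyloid, from a 1-KM of 20% without. The apparent gap is 36.0 − 20.0 = 16.0 points. The true gap is 28.72 − 18.31 = 10.4 (s = 1) or 32.07 − 19.13 = 12.9 (s = 0.5).

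**Can the order reverse?** At equal admission hazards the excess depends only on sλ. It is larger with amyloid unless the amyloid share is below 0.0932/0.2554 = 36.5% of the other cohort's share. With shares of 30% v 100% and 1-KM of 30%, the excess is 2.1 v 2.5 points. With the same shares and a doubled admission hazard, the true gap is 15.3, still below 16.0.

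**If 17% is the overall rate.** The non-amyloid rate is (0.17 − 0.15 × 0.40)/0.85 = 12.9%. At 1-KM of 20% and s = 1 the excess is then 4.2 v 1.3 points instead of 4.2 v 1.7, so the contrast widens.

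**Cardiovascular death.** With an assumed cardiovascular share c of deaths, the excess is [1 − exp(−2cλ)] − c[1 − exp(−2λ)]. That is 2.5 v 0.4 points (amyloid v none) at c = 0.5, and 0.9 v 0.1 at c = 0.9.

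**Against sampling error.** 15% of 321 is about 48 amyloid patients. At 30% the 95% half-width is 1.96 × √(0.3 × 0.7/48) = 13 points.

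**The extension.** With 48 v 273 patients and observed mortality of 40% v 17%, the pooled two-proportion z is 3.6. Schoenfeld's approximation, with 48 × 0.40 + 273 × 0.17 = 65.6 deaths, gives ln(2.74) × √(65.6 × 0.15 × 0.85) = 2.9. Both are significant.

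**The case against.** The strongest reply is that the error needs three steps that the plan never states: admission analysed alone, deaths censored, and 1-KM reported as a risk. The one named example, event-free survival, is naturally read as counting death, and the summary puts death and readmission under one main event. Under such a composite there is no bias. This stands as a limit: the documents leave the choice open and do not commit to the faulty analysis. But event-free survival is only an example, cardiovascular mortality is also named, and the secondary objectives analyse pacing separately, so separate curves are a real possibility.

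Second, the planned effect measures are not harmed. A reader might infer that the log-rank test or the hazard ratio is biased. It is not: with deaths censored, both compare cause-specific hazards. Crude 2-year proportions with complete follow-up are also unaffected. This stands in full.

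Third, the size rests on assumed admission rates, and s = 1 is an extreme. The introduction says that amyloid "presents itself with symptoms of heart failure, orthostatic hypotension, and syncope", so a smaller share of its deaths may come before an admission. This also stands. It is why the range starts at s = 0.5 and why the larger error with amyloid is only probable.

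Finally, because "if not significant; monitoring would continue up to 3 years", a reader might carry the 40% v 17% hazards to 3 years and quote larger errors. The documents do not support that: the extension follows a non-significant 2-year result, which those mortality rates would not give. Only the direction holds: for given hazards, the bias grows with follow-up.

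**Conclusion.** The point holds conditionally. For heart-failure admission or cardiovascular death analysed alone with competing deaths censored, 1-KM cannot fall below the Aalen-Johansen estimate in any dataset, and it exceeds it when competing deaths precede later events. That direction needs no assumption about hazards; the size does. For admission it is about 1 to 6 points with amyloid and 0.4 to 2.5 without. For cardiovascular death it is about 0.9 to 2.5 v 0.1 to 0.4, with an assumed cardiovascular share of 90% down to 50%.

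These figures rest on the plan's mortality, constant independent hazards and assumed admission rates. They also take 17% as the non-amyloid rate, although the plan states it for TAVI patients in general. The bias is smaller than the sampling error in the amyloid cohort, but it always runs one way within a cohort and is avoidable. The change should be made; the all-cause mortality comparison is not in doubt.

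**What to change.** In section 10.1:

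1. State that event-free survival counts all deaths as events. Keep Kaplan-Meier and log-rank for it and for all-cause death.
2. For heart-failure admission, report Aalen-Johansen cumulative incidence by cohort with death as the competing event. For cardiovascular death do the same, with non-cardiovascular death as the competing event.
3. Show the cumulative incidence of the competing death beside each curve. At equal admission hazards (1-KM 30%, s = 1), admission alone reads 23.8% with amyloid v 27.5% without. Amyloid looks protective until death without admission, 34.2% v 14.4%, is shown next to it.
4. Keep Cox as the main comparison for these outcomes and label its result a cause-specific hazard ratio; the section now calls the Cox output an odds ratio.

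The cost is a few sentences and standard software. No visits are added, since dates of death and admission and cause of death are already needed for the primary objective. The downside is slightly lower reported percentages and one more curve per figure.
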